9.3.3 Pregnancies and pregnancy outcome

All available records related to pregnancies and pregnancy outcomes including diagnoses (based on ICD-10 coding tests and exams usually performed during a specific trimester) will be searched in databases, if available, as follows (see code list in Appendix 3).

- Pregnancies
 - Pregnancy records (date of record)
- Pregnancy outcomes
 - Outcomes of pregnancies (i.e., live births, termination, stillbirth, miscarriage, or recorded birth defect), if information is available in the data source

If information on the timing of the pregnancy is available (e.g., date of delivery, last menstrual period (LMP), trimester information), it will be considered for the estimation of the beginning of the pregnancy. The availability of such information may differ by data source.

In case no information is available permitting the analysis of the timing of the pregnancies, the method for calculating the timing of pregnancies, which is published for the specific data source, will be used. In case there is no approach published, the first pregnancy record minus 90 days, which mark the end of the first trimester and generally will be time of the pregnancy when a first check-up will have been performed, will be considered as the estimated start of the pregnancy. This approach was endorsed by the PRAC for another PASS (see for example Valproate, EUPAS11379).

9.4 Data Sources

All information on exposure and outcomes will be derived from established secondary longitudinal data sources.

Data sources are considered for the DUS based on a sufficient number of patients on oral retinoids and the availability of information relevant to describe the effectiveness of the updated PPP. Based on these criteria the following data sources will be considered (see Table 3 for more detail):

- SNIIRAM of the SNDS in France
- Collective of insurants from company health insurance funds in Germany
- SIDIAP in Spain
- National Health registers in Sweden

Table 3: Summary of various databases being considered for the DUS

Country	France	Germany	Spain	Sweden
Name and Type	SNIIRAM of the SNDS Claims database	Company Health Insurance funds Claims database	SIDIAP Sistema d'Informació per al Desenvolupament de la Investigació en Atenció Primària. Information System for Research in Primary Care	National Health registers National Drug-, Patient- and Birth registers
Overall representativeness	~88% of French population	~6% of German population	>80% of Catalanian population	National coverage for Sweden

Size	57 million, all health insurance schemes in office-based care and hospitalization	5 million insureds	About 5 million active people and about 7 million active, transferred and dead people	10 million, specialist and hospital out and in-patient care and all drugs dispensed for the Swedish population
Data available since	2009	2004	2005	2005 (1997)
Data lag time	9 months	12 months	One year	1 - 9 months (depending on the type of registry)
Patient age	Available	Available	Available	Available
Diagnosis	Available in the hospital setting; ICD-10 codes	Available; ICD-10 codes	Available ICD-10 codes	Available; ICD-10 codes
Information on physician visits	Available	Available	Available	Available
Records of laboratory pregnancy tests (for example via ICD-10 codes)	Human chorionic gonadotropin (HCG) blood tests performed	Available	Available (mainly urine pregnancy tests)	If ICD-10 code, it could be captured
Prescriptions of oral contraceptives or IUDs	Only reimbursed contraceptives	Only reimbursed contraceptives	Available	Available
Drug information for oral retinoids (date of prescription, pack size, strength)	Available; duration approximated algorithmically	Available; duration approximated algorithmically	Available	Available; duration approximated algorithmically
Pregnancy	Available	Available	Available	Available

9.4.1 Claims data – France and Germany

9.4.1.1 France – SNDS

The SNDS (Système National des Données de Santé) is a claims database, following the National Health Insurance expenses. The primary purpose of the SNDS is to determine the

costs for all National Health Insurance System schemes in office-based care (SNIIRAM databases) and hospitalisation (PMSI databases) individualized by beneficiary.

The SNDS database is a very exhaustive option for France. It is a claims database covering all the Health Insurance schemes based on individuals' employment status in office-based care and hospitalisation and is individualized by beneficiary. The general health insurance plan covers employees in the industry, business, and service sectors; public service employees; and students, accounting for approximately 88% of the French population.

With this very large sample size (57 million beneficiaries of the French General scheme, the SNDS allows to have a comprehensive and detailed health information, relevant and very useful for epidemiological and health economic studies (Tuppin 2017). The RWES/Health Economics and Outcomes Research department of IQVIA France is now able to conduct this study, upon authorization, for SNDS access.

The vast majority of pregnancies and pregnancy outcomes are covered in the SNDS. In 2018, an algorithm was published to identify pregnancy episodes in the French health care database (Blotière 2018).

The SNDS database was used to evaluate the compliance with PPP recommendations in women of childbearing potential exposed to retinoids. The study included about 9000 women initiated on acitretin in France (Raguideau 2015).

The data of medical services listed all the closing transactions related to the payment of services to the beneficiaries. These files include information related to the care recipient, the type of care giver, the type of care and the monetary flows induced. However, in these files of medical services, some health consumptions cannot be seen, such as consumptions not claimed for reimbursement, not reimbursable health services or self-medication.

Now, the historical coverage of the SNDS is as large as the EGB (General sample of beneficiaries), but as the database was enriched each year, we recommend to not go further back than 2009. The choice of the study period coverage needs to be justified.

9.4.1.2 Germany – Collective of insurant from company health insurance funds

For this study, a collective of insurants from company health insurance funds will be used. The analysis will be done by Team Gesundheit, Gesellschaft für Gesundheitsmanagement GmbH, based in Germany.

Data are currently available from 2004 to 2016 (as of January 2018) and contain over 5 million insured patients representative of the entire insured German population with a coverage of about 6%. The privacy of patients in the database is protected at all times and the information cannot be used for re-identification of patients.

The database allows for the analysis of patient-level demographic and clinical characteristics, healthcare resource utilisation (e.g., number and/or duration of inpatient and outpatient visits), and dated prescriptions.

The coverage of pregnancies in women receiving health care services is high because all reimbursable services are comprehensively recorded in the claims data. The completeness of outcomes reporting varied depending on the type of outcome, e.g. an underreporting of induced abortions is possible (Mikolajczyk RT et al. 2013). Pregnancies will be identified in accordance with the approach published by Mikolajczyk et al.

The database also allows comparisons between patient and control groups with respect to specific utilisation of health care services.

Longitudinal pre-index and follow-up periods can also be defined according to the study requirements. Diagnoses and procedures are coded using ICD-10 (German modification), and include treatments that are reimbursed in accordance with the German law.

Among others, the following measures are available in the German database allowing demographic characteristics, treatments, healthcare utilisation and clinical outcomes to be assessed:

- Registration data including age, gender, insurance status, time insured, and region of residence
- Outpatient care data including ICD-10 diagnoses, physician specialty
- Inpatient care claim including ICD-10 diagnoses (up to 3 principal and 30 secondary diagnoses per stay), billed diagnosis related groups (DRGs, German classification), up to 30 OPS-Codes per stay, duration of hospitalizations, and medical department; drugs captured via OPS code
- Code of prescribed medications and related costs, PZN (Pharmazentralnummer) of prescribed medications, and date of prescription

German claims databases cover all reimbursed contraceptives. In 2016, 1.1 million females in the age group 13 to 49 year were captured in the company health insurance database. Thereof, 7% had records of contraceptives for topical use (ATC G02B) or for systemic use (G03A). Preliminary data revealed that 16% of the women receiving oral retinoids used contraceptives concomitantly. Although contraceptives can be reimbursed if contraception is medically indicated, only 2% of the women above the age of 20 had a record of contraceptives (data on file). Before the 29th March 2019, prescribed contraceptives in Germany were only reimbursed for women under the age of 20. Since then, the age limit has been increased to 22 years.

To the best of our knowledge, there is no other type of data source which provides such comprehensive information across the health care setting in Germany suitable to be used as data source for this DUS to address the study objective.

An electronic medical record (EMR) database available for Germany, Disease Analyzer, is not a suitable option in this case because patients cannot be tracked across different physician specialties. This makes it impossible to track patients from a dermatologist who prescribes oral retinoids to the gynaecologist who prescribes contraceptives and monitors women during pregnancies.

9.4.2 Primary care database – Spain

9.4.2.1 Spain – SIDIAP

SIDIAP contains data of anonymized healthcare records for nearly 5.8 million people who receive primary care in one of the primary care centers of Catalonia, representing approximately 80% of the Catalonian population. SIDIAP covers 274 centers and

approximately 3,400 GPs. SIDIAP is highly representative of the population of Catalonia in terms of geographical, age, and sex distributions (Bolibar et al., 2012). Data is collected by health professionals during routine visits in primary care:

- Electronic medical records (EMR) captured using the e-CAP platform at the center-level: demographics, primary care appointments, diseases (ICD-10), clinical variables, prescriptions, immunizations, and derivations.
- Laboratory results: since 2006 all laboratory results are included.
- Prescribed medication: since 2005 all prescribed medicinal products with the national healthcare system are included in the database.

Laboratory pregnancy testing, contraception, and pregnancy outcomes are covered in the SIDIAP database for women of childbearing potential aged 13-49. The way of calculating the beginning of a pregnancy is standardized in daily clinical practice, which includes laboratory pregnancy tests, last menstrual period and other confirmation criteria (Aliaga et al., 2018). Approximately 66% of all term pregnancies in Catalonia were recorded in SIDIAP during the period in which the study was conducted by Aliaga et al.

A study published in 2011 reported a prevalence of contraceptive use (including hormonal contraceptives, condoms, and IUDs) of approximately 86% in sexually active adolescent to young women (ages 16-29) (Carrasco-Garrido et al. 2011). The most commonly used method of contraception was the condom followed by hormonal contraceptives. Only some of the hormonal contraceptives are reimbursed and therefore recorded in SIDIAP.

To guarantee the quality of the data, a scoring system is applied. Primary care practices with ready data that is ready to be used for research can be selected based on the completeness of their records captured using the e-CAP platform. It is estimated that the data assigned to 40% of the professionals with the highest scores (coverage of 1.9 million people) is adequate to conduct high quality studies. This population sub-group is known as SIDIAP-Q. This group is representative of the Catalanian population (Garcia-Gil et al., 2011).

SIDIAP has been used extensively in medical research including DUS since 2010 across Europe and has been found to be a valid source for research (Wilson et al, 2015). A study on the association between effective disorders presenting before and during pregnancy considering the use of medication has recently been published in 2018 (Aliaga et al., 2018).

9.4.3 National registry data - Sweden

9.4.3.1 Sweden – National Registries

IQVIA suggests creating a linked research database for Sweden with full national coverage through combining data from the National patient register, covering all specialist

and hospital care in Sweden, with the National drug register, covering all drugs dispensed at pharmacies in Sweden, and the Medical Birth register covering all pregnancies resulting in delivery.

With the linkage (done via a unique identifier) between these registries, a comprehensive longitudinal view of health care provided in Swedish secondary care and above and drugs dispensed will be provided. This longitudinal data enables the study of historical clinical information on the subjects treated with oral retinoids. The proposed data sources will not provide clinical anamnesis and lab results for the patients, nor information on the care provided for the patients in the primary care setting.

Individual patient data is collected from both in- and out-patient hospital-based specialist care across all of Sweden. The National Patient Register dates to 1964. From 1987 there is information on all completed in-patient admissions across the country. The collection of out-patient care data began in 2000. The register is updated annually and available from September/October the following year.

The available data in the National Patient Register include:

- Patient demographics (age, gender)
- Clinical information: diagnoses (ICD-10 code and associated position), DRG code, care setting (inpatient or outpatient), admission date and discharge date (for inpatient care), surgeries and procedure performed)
- Hospital information: region, clinic, etc.

Information on patient anthropometrics (height, weight, etc.) and lifestyle (smoking, etc.) is not available through the National Patient Register, nor are laboratory and clinical measurements as blood pressure and blood lipid levels. In addition, information on drugs administered at the hospital is not available. Again, this type of data could be captured from EMRs.

All medicines are prescribed electronically in Sweden. The National Prescription Register tracks the full details of all dispensed medications at individual patient-level in Sweden since July 1, 2005. Patients are followed longitudinally through their personal identification number, regardless of which pharmacy they visit. The National Drug Register is updated monthly and covers all sales from Swedish pharmacies.

The available data in the National Drug Register include:

- Patient demographics (age, gender, and residency)
- Prescription information (date of prescription, prescriber's specialty, WHO ATC code, and brand name)
- Dispatch information (dispatch date, product number, total dose dispatched, number of packages dispatched, and drug cost)
- Product information (Package size, formulation, etc.)

Information on prescribed dose is only documented in free text format where available, and days' supply is not recorded.

In Sweden, the online database on prescription held by the National Board of Health and Welfare provides the following information on the annual prevalence of Swedish women aged 15-49 years who filled at least one prescription for hormonal contraceptives in 2012-2017: ATC G02B contraceptives for topical use: 4.3-5.4%; ATC G03A hormonal contraceptives for systemic use: 22.4-26.1% (reference: prescription registry).

Of note, to gain access to the linked register an approval from the local ethical review board is necessary, whereby the research project and ethical aspects should be explained in a formal application. The ethics approval is dependent on the data being made publicly available in some form. Please see below for more detailed information on the information contained in each register.

The Medical Birth Register contains information on 97% to 99.4% of all pregnancies resulting in delivery in Sweden and is frequently used for quality work and for research (National Board of Health and Welfare, Sweden 2012; Olausson PO, 2002). The register contains detailed information about mothers and new-borns. However, pregnancies are only captured after 22 weeks. The identification and timing of pregnancies will be done according to published methodology (Stephansson et al. 2018).

Records on pregnancies are also documented in the National Patient Register regardless of the duration of pregnancy, but missing information regarding early termination needs to be taken into account.

9.5 Study Sample Size

The aim of this study is to provide a description of real-life treatment patterns. The final study sample size is driven by the patient numbers available in the data sources in the target countries.

The sample size is calculated in order to ensure that the study obtains meaningful data for descriptive purposes.

9.5.1 Determination of sample size

The sample size calculation is determined by the desired accuracy/precision of the estimation by confidence interval (CI) of the observed proportions for the variables relevant to address the primary objective. As the observed percentage (p) is not known in advance, we consider it to be 50% (maximum uncertainty).

Table 4 shows that to achieve a sufficient accuracy, i.e. within a margin of accuracy +/- 5%, of the estimation by a two-sided 95% CI for a proportion (p) 50 %, a sample size of 385 patients is required, for a proportion (p) 20% (80%) 246 patients. The precision for an

observed percentage with 95% CI will be determined by the formula below (normal approximation):

$$e = \sqrt{\frac{p(1-p)}{n}} \times \varepsilon_{\alpha}$$

With n sample size, p observed percentage, ε_{α} 1.96 for 95% CI, e Precision.

Table 4: Required number of patients by acceptable precision (95% CI) or proportions (normal approximation)

Precision	Observed percentage (accuracy): p(1-p)				
	10% (90%)	20% (80%)	30% (70%)	40% (60%)	50% (50%)
± 2.0%	865	1537	2017	2305	2401
± 3.0%	385	683	897	1025	1068
± 4.0%	217	385	505	577	601
± 5.0%	138	246	323	369	385
± 6.0%	97	171	225	257	267
± 7.0%	71	125	165	189	196
± 10.0%	35	62	81	93	97

9.5.2 Sample Size for target countries

A feasibility count in the individual target countries showed that the data sources are able to provide a sufficient number of patients (see Table 5) for the analyses (see section 9.7 Data Analyses for details).

The numbers of females of childbearing potential receiving oral retinoids were checked for a 3-year period (2015-2017) in Germany, Spain, and Sweden. The number of patients meeting the inclusion criteria are 3,729 in Germany, 4,800 in Spain, and 20,580 in Sweden.

In France, only the number of boxes that was reimbursed in France in total (without any restriction to age and gender) is available without receiving ethical approval for the study;

the number of 1,041,500 boxes in one year suggests that the number of women of childbearing potential will be sufficient for analysis.

Table 5: Oral retinoids in target countries - number of patients or prescriptions

		France SNDS ¹ 2016	Germany Claims Data ² (2013 – 2015)	Spain SIDIAP (2015-2017) ³	Sweden National registry ⁴ (2015-2017)
Number of patients, total		n.a.	3,729	4,842	20,580
By substance	acitretin	n.a.	153	281	442
	alitretinoin	n.a.	100	15	--
	isotretinoin	n.a.	3,492	4,546	20,138
Number of prescriptions, total		1,041,500	n.a.	n.a.	67,932
By substance	acitretin	195,417	n.a.	n.a.	1,283
	alitretinoin	15,036	n.a.	n.a.	--
	isotretinoin	831,047	n.a.	n.a.	66,225

¹ Number of boxes reimbursed; total, no restriction with respect to age and gender, ² Unique female patients aged 13-49, ³ Female patients, 13 to 49 years, ⁴ Non-unique female patients aged 15-49; n.a.: not available before analysis

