9.7.1 General Considerations

Given the study objectives the analyses will be mainly descriptive and will be conducted by country, by active substance and study time periods (both pre-implementation periods and post-implementation period). To allow for analysis across all data sources used in the study, a meta-analytic approach will be used to assess and pool the results from the four study countries together for each active substance (see 9.7.3.4).

The analyses will be provided for the overall class of oral retinoids and for the single active substances. Categorical variables will be presented as counts (n), proportions (%) with CI where relevant as for parameters used to address the primary objective and for the comparison of the incidence of exposed pregnancies. Continuous variables will be presented as means with standard deviation (SD) and as medians with interquartile range (IQR), where appropriate.

Changes in the reimbursement policy for contraceptives in the healthcare systems of the study countries will be considered to discard any differential misclassification of exposure.

The statistical unit will be the oral retinoid treatment episode and patient as well as prescription where appropriate. Patients who have multiple treatment episodes of oral retinoid use will be entered the cohort for analysis more than once.

The term “use” in the context of the analysis refers to the prescription or dispensing of drugs or IUD.

In the analysis, prescriptions of patients will be followed from the exposure start date to censoring date, i.e., transfer out of the database incl. death or the end of the study period, whichever comes first.

Statistical analyses will follow the tables shells validated by the MAH consortium and will be displayed using tables, listings and/or graphs. The statistical analysis will be conducted using SAS or an equivalent statistical analysis software. A detailed statistical analysis plan (SAP) will be prepared prior to data extraction.

The statistical results of all target countries and all active substances will be presented in a single report.

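### Section 9.5.2 calls patient numbers sufficient, but its counts miss the protocol's own 385-patient criterion for acitretin and alitretinoin in Germany and Spain, and that criterion does not cover the before-after difference

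*Protocol*

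**What the plan says.** Section 9.5.1 bases the sample size on the precision of the proportions that address the primary objective. Accuracy is sufficient when it lies "within a margin of accuracy +/- 5" per cent; at a proportion of 50%, "a sample size of 385 patients is required". The requirement at 20% or 80% is 246. Table 4 extends this to other precisions, always for one proportion.

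Section 9.5.2 then concludes: "A feasibility count in the individual target countries showed that the data sources are able to provide a sufficient number of patients". It points to Table 5 for the counts and to Section 9.7 for the analyses. Section 9.7.1 runs those analyses by country, substance and study period: "The analyses will be provided for the overall class of oral retinoids and for the single active substances". Section 9.1 compares a two-year pre-referral period with a post-implementation period of about two years.

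On the source of the counts, Section 9.5.2 says: "The numbers of females of childbearing potential receiving oral retinoids were checked for a 3-year period (2015-2017) in Germany, Spain, and Sweden". It describes the 20,580 Swedish patients as meeting the inclusion criteria, which set an age range of 13 to 49. The Table 5 footnote describes the same figure as "Non-unique female patients aged 15-49", and the German column of Table 5 is headed 2013–2015.

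**The concern.** The protocol sets a numerical criterion, prints the counts, and declares them sufficient for analyses that split the data by substance. For two of the three substances the printed counts do not support that declaration in Germany or Spain. The criterion also measures something other than the primary question: a change between two periods carries the sampling error of both.

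What is at stake is interpretation. Section 7.1 itself calls the difference between the old and updated programme relatively small. A reader who trusts the sufficiency statement could take an unchanged percentage among acitretin or alitretinoin users in Germany or Spain as evidence that the update had no effect, when the interval would be too wide to show that.

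**Working it through.** **The plan's own figure.** n = 1.96² × p(1−p) / e². With p = 0.5 and e = 0.05: 3.8416 × 0.25 / 0.0025 = 384.2, so 385. With p = 0.2: 245.9, so 246. Both agree with Section 9.5.1, and all of Table 4 reproduces to within one patient. There is no arithmetic error here.

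**Inputs.** Three-year patient counts from Table 5; two-year comparison periods from the Abstract and Section 9.1; p = 50% as in Section 9.5.1.

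**Formulas.** Half-width for one proportion: 1.96 × √(0.25/n). Half-width for the difference between two independent periods of n each: 1.96 × √(0.5/n).

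**Difference at the plan's criterion.** At n = 385 per period: 1.96 × √(0.5/385) = 7.06 pp. For ±5 pp: 3.8416 × 0.5 / 0.0025 = 768.3, so 769 per period.

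**Achieved precision.** The two-year count is the Table 5 count × 2/3. This assumes steady, proportional accrual, which the protocol does not state. If every patient counted were a distinct long-term user, the two-year count would equal the printed one. The last column therefore runs from the printed to the scaled count.

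| Cell | 3-year count | One proportion, printed count (pp) | 2-year count (× 2/3) | One proportion, 2-year count (pp) | Difference, printed to 2-year count (pp) |
|---|---|---|---|---|---|
| Acitretin, Germany | 153 | 7.9 | 102 | 9.7 | 11.2 to 13.7 |
| Acitretin, Spain | 281 | 5.8 | 187 | 7.2 | 8.3 to 10.1 |
| Acitretin, Sweden | 442 | 4.7 | 295 | 5.7 | 6.6 to 8.1 |
| Alitretinoin, Germany | 100 | 9.8 | 67 | 12.0 | 13.9 to 17.0 |
| Alitretinoin, Spain | 15 | about 25 | 10 | about 31 | about 36 to 44 |
| Isotretinoin, Germany | 3,492 | 1.7 | 2,328 | 2.0 | 2.3 to 2.9 |
| Isotretinoin, Spain | 4,546 | 1.4 | 3,031 | 1.8 | 2.1 to 2.5 |
| Isotretinoin, Sweden | 20,138 | 0.7 | 13,425 | 0.9 | 1.0 to 1.2 |

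The Spanish alitretinoin figures are only indicative, because the normal approximation is poor at 10 to 15 patients.

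**Swedish acitretin.** 442 exceeds 385 as printed. Since 385/442 = 0.87, the criterion still holds if at least 87% of the 442 are distinct and appear in a two-year window. The plausible range is about 295 to 442 if all are distinct, and possibly below 295 if patients were recounted.

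**Isotretinoin in Sweden despite non-unique counting.** Even if each patient had been counted three times (an assumption), 20,138/3 ≈ 6,713 remain, well above 769.

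**Sensitivity to p.** At p = 20% (requirement 246), Spanish acitretin passes as printed (281) but not when scaled (187), and Swedish acitretin passes even at 295. German acitretin and both alitretinoin cells still fail. Section 9.4.1.2 reports 16% concomitant contraceptive use among German retinoid users. At that value ±5 pp needs 3.8416 × 0.16 × 0.84 / 0.0025 = 206.5, so 207, against 153 and 100.

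**The case against.** The study is mainly descriptive, uses every available patient, and lets the databases set its size (Sections 9.5 and 9.7.1). Nothing states 385 as a minimum for each country-by-substance-by-period cell. Isotretinoin makes up 94% to 98% of the patients counted, so the bulk of the comparison is precise. Small cells are also to be pooled across countries by substance (Section 9.7.3.4).

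Much of this stands, and it limits the consequence to what the protocol claims. It does not rescue the claim itself, because Section 9.5.2 asserts sufficiency for analyses that Section 9.7.1 splits by substance. Pooling helps only in part. Simple sums without France give 876 × 2/3 = 584 for acitretin (difference ±5.7 pp) and 115 × 2/3 ≈ 77 for alitretinoin (±15.8 pp). France may add a great deal: Section 9.4.1.1 mentions an earlier study in the same database with about 9,000 women starting acitretin. But Table 5 gives France only as boxes, for all ages and both sexes.

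Two further criticisms are tempting, and the protocol does not support them. A reader might infer that the interrupted time series is planned without enough data for the small substances. Section 9.7.3.5 makes it conditional on at least 6 time points per period and 100 observations per point, so it would simply not be run. A reader might also infer from "Patients who have multiple treatment episodes of oral retinoid use will be entered the cohort for analysis more than once" that the reported intervals will be too narrow. The variance method can properly be left to the analysis plan, many main outcomes are percentages of patients, and the protocol gives no re-entry rate or within-patient correlation from which to size any effect.

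**Conclusion.** The point holds as an internal inconsistency. Four cells miss the protocol's own criterion as printed, with no scaling: acitretin and alitretinoin, each in Germany and Spain. Swedish acitretin probably misses it over a two-year period, but this rests on the 2/3 assumption or on the unknown amount of recounting. Separately, the criterion says nothing about the precision of the before-after difference.

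Two stronger readings should be avoided. It would be wrong to say that these substances fail in every country counted: Swedish acitretin passes as printed, Sweden has no alitretinoin count, and France has no patient count at all. It would also be wrong to say that ±5 pp on the difference is reached nowhere: isotretinoin exceeds 769 per period in Germany, Spain and Sweden, and so does the overall class (3,729, 4,842 and 20,580, or about 2,486, 3,228 and 13,720 after scaling).

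The labelling faults stand whatever view is taken of precision. The Swedish figure cannot be said to meet the inclusion criteria when it is non-unique and starts at age 15, and the German count carries two different sets of years.

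**What to change.** - In Section 9.5.2, limit the sufficiency statement to isotretinoin and the overall class in Germany, Spain and Sweden. Say that France has box counts only, so its precision cannot yet be stated.
- Add a table of achieved half-widths by country and substance, for the single proportion and for the before-after difference, with the scaling to two years stated as an assumption.
- State that country-level acitretin and alitretinoin results in Germany and Spain, and probably acitretin in Sweden, do not reach the stated precision, so a finding of no change there is not evidence of no effect.
- Label the Swedish count as non-unique and aged 15–49, and remove the statement that it meets the inclusion criteria.
- Reconcile the German count years between the text (Section 9.5.2 and the Abstract, 2015–2017) and Table 5 (2013–2015).

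The cost is a rewritten subsection and one table. No additional patients, data or analyses are needed; the stated precision simply becomes less favourable for the smaller substances.
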